12.5.10.3 Temporary Suspension of Enrollment for ad hoc DSMB Safety Review

A temporary halt in enrollment will be implemented if an ad hoc DSMB safety review is required.

13. STATISTICAL CONSIDERATIONS AND ANALYTICAL PLAN

13.1 Overview

The primary objective of this proposal is to conduct a prospective, non-blinded randomized trial comparing rates of remission of novel empiric elimination dietary therapies in eosinophilic esophagitis (EoE) in order to assess the therapeutic viability of empiric elimination diets. Moreover, we aim to assess response to topical swallowed steroids in non-responders to empiric dietary therapy regimens. Participants aged 18 to 60 years with active EoE will be enrolled and the primary efficacy outcome will be the rate of histologic remission assessed using esophageal biopsies obtained following a six week randomized trial of one of two empiric diets. During the screening process, active EoE will be confirmed by histologic evaluation of esophageal biopsies obtained during an esophagogastroduodenoscopy (EGD) in subjects with a history consistent with EoE.

13.2 Endpoints/Outcomes

The primary efficacy endpoint will assess and compare the percentage of patients achieving remission by following the two diets. Pre- and post-therapy peak eosinophil counts per hpf and percentages of patients that attain histologic remission (<15 eosinophils/hpf) will be reported.

A variety of secondary endpoints, including more detailed histologic and endoscopic scores, novel biomarkers, and several Patient Reported Outcome (PRO) measures will also be assessed. In addition, we will assess the possible value of a variety of clinical characteristics and biomarkers in terms of predicting response to therapy. This study will provide significant novel information. This will be a prospective dietary therapy trial using these empiric elimination diets. As part of our secondary aims, we will also be utilizing a number of novel potential biomarkers to assess their ability in predicting and assessing response to therapy as well as a number of PRO metrics.

13.3 Measures to Minimize Bias

Patients will be randomized using a 1:1 scheme to 1FED or 6FED within each investigative site. Study staff will remain blinded to the randomization plan so they do not know the upcoming treatment assignment will be for a patient until after the patient has been assigned. Study personnel who will perform the histologic assessments will be blinded to treatment assignment for the slides they are evaluating. The CRPC will not be told which diet a

participant has been assigned to, and they will not receive any information or documentation indicative of dietary assignment. The slides and/or images of slides provided to the CRPC will not contain any information that reveals which diet the participant is on. Knowledge of dietary assignment will be limited to study staff who need to know which diet a participant has been assigned to (i.e. dietitians).

13.4 Analysis Plan

13.4.1 Analysis Populations

The analysis population for the primary and key secondary endpoints will be the intent-to-treat population. All patients that have been randomized will be included in this analysis. Patients for which the primary endpoint of histological remission cannot be determined will be imputed as treatment failures.

13.4.2 Primary Analysis of Primary Endpoint(s)/Outcome(s)

The primary endpoint for this study will be histologic remission (<15 eosinophils/hpf) determined at the end of Phase 1 and will be compared between the two treatment groups. The formal statistical hypothesis for the primary endpoint is:

$$H_0: p_{1FED} = p_{6FED}$$

$$H_1: p_{1FED} \neq p_{6FED}$$

where

p_{1FED} = percentage of patients in histologic remission (<15 eosinophils/hpf) on the 1FED diet at end of Phase 1

p_{6FED} = percentage of patients in histologic remission (<15 eosinophils/hpf) on the 6FED diet at end of Phase 1

This hypothesis will be tested using the generalized linear mixed effects model with the logit link (for binary outcome) that accounts for the clustering within sites. Important covariates to be included in this model are sex, presence of atopy and duration of disease. All tests will be conducted at $\alpha=0.05$.

The mixed effects model is planned in order to include the site as a random effect in the model. This approach assumes the sites included in this trial are representing a sample of sites about which we wish to make inferences and therefore will include site as a random effect instead of a fixed effect that implies we are only making inferences about those specific sites in the study.

13.4.3 Supportive Analyses of the Primary Endpoint(s)/Outcome(s)

Sensitivity analyses will be conducted to assess the robustness of the results. A chi-square test without covariate adjustment will be performed to compare the histologic remission rates at the end of Phase 1 between the two groups. As a second sensitivity analysis, additional covariates will be included in the generalized linear mixed effects model described above including PPI use at baseline, race and/or ethnicity and anthropomorphic measures. Forest plots displaying differences in remission rates along with two-sided 95% confidence intervals for subgroups defined by categorical covariates will be provided to visually examine the consistency of results among subgroups.

As an additional sensitivity analysis, multiple imputation (MI) for patients who are missing the primary outcome measure will be performed. The missing data mechanism will be investigated to determine if the data are missing

at random. In addition, a complete cases analysis will be conducted to investigate consistency of the conclusions from those who complete the study in comparison to conclusions from the intent to treat population with imputed values using the “set to failure” approach and also the MI approach.

All sensitivity analyses will be conducted at the nominal two-sided $\alpha=0.05$.

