13.4.4 Analyses of Secondary and Other Endpoint(s)/Outcome(s)

Following are the secondary objectives of the study:

1. To extend Phase 1 of this study with a prospective non-blinded trial that determines the rate of remission following SGC in the 6FED non-responders and the rate of remission following 6FED in the 1FED non-responders (Phase 2).
2. To evaluate the effect of each therapy on histological remission defined by a variety of changes in eosinophils, including (a) pre- and post-therapy peak eosinophil counts; (b) partial remission (2-14 peak eosinophils/hpf); and (c) complete histological remission (≤ 1 peak eosinophils/hpf).
3. To evaluate the effect of each therapy by utilizing the histology scoring system (HSS) created to express the severity and extent of other abnormalities in the gastrointestinal (GI) tract that often accompany eosinophilic inflammation.
4. To evaluate endoscopic outcomes as assessed by the endoscopy scoring system (EREFS).
5. To determine the impact of each therapeutic intervention on biomarkers using the EoE Diagnostic Panel (EDP).

For secondary objective 1, the remission rate for non-responders who proceed to Phase 2 will be summarized separately depending on the treatment patients received during Phase 1. The 95% two-sided confidence interval for the rate will be provided. In addition, forest plots that display the estimated remission rate along with two-sided 95% confidence interval will be presented for the subgroups as defined for the primary endpoint. This will provide a visual representation to assess consistency of rates across subgroups. If the remission rate is missing for patients in Phase 2, it will be imputed as a treatment failure.

The formal statistical hypothesis for each of the key secondary endpoint is:

$$H_0: \theta_{1FED} = \theta_{6FED}$$

$$H_1: \theta_{1FED} \neq \theta_{6FED}$$

where

θ_{1FED} =population parameter (e.g. mean, proportion) for patients in histologic remission (<15 eosinophils/hpf) on the 1FED diet at end of Phase 1

θ_{6FED} =population parameter (e.g. mean, proportion) for patients in histologic remission (<15 eosinophils/hpf) on the 6FED diet at end of Phase 1.

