13.6 Sample Size Considerations

The sample size was based on the primary endpoint of the percent of patients in histologic remission (<15 eosinophils/hpf) at the end of Phase 1. Based on preliminary data, it is assumed that the remission rate for the 1FED population is 45%.¹⁶ We assume that the remission rate in the 6FED population will be increased to 70%. A sample size of 60 patients per group (120 total patients) will provide at least 80% power to detect a difference in rates between groups of 25% at the two-sided $\alpha=0.05$. This calculation is based on a likelihood ratio test statistic for comparing proportions. To allow for a potential approximate 15% drop-out, the sample size will be increased to 68 patients per group (136 total patients). This calculation was performed using the PASS vers. 12 software. The following table displays the robustness of the sample size under various response rate and drop-out rate scenarios.

Sample Size per group	Difference to detect with 80% power if 1FED rate is 45%	Difference to detect with 80% power if 1FED rate is 50%	Difference to detect with 80% power if 1FED rate is 55%
56	26%	24%	24%
60	25%	23.5%	23.5%
64	24%	23%	23%
68	24%	23%	22%

14.IDENTIFICATION AND ACCESS TO SOURCE DATA

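### Subgroup consistency of the diet effect is to be judged by eye, with no interaction estimate and no rule for reading the plot, and the SAP does not say whether the plots are kept

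*Protocol*

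**What the plan says.** Protocol section 13.4.3 (supportive analyses of the primary endpoint) states that forest plots of differences in remission rate, with two-sided 95% confidence intervals, "for subgroups defined by categorical covariates will be provided to visually examine the consistency of results among subgroups". No other method for judging consistency of the diet effect is given, and no criterion for inconsistency.

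The models do not fill the gap. The primary model (protocol 13.4.2; SAP, Analysis of Primary Outcome) and the secondary models (protocol 13.4.4; SAP, Analyses of Secondary Endpoints) list covariates as main effects only. The exploratory analyses relate markers to remission (protocol 13.4.5) or compare responders with non-responders (SAP). They ask who responds, not whether the difference between diets varies across patients.

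The SAP, dated 10/14/2019, contains no forest plots and no subgroup analysis of the diet effect. It neither keeps nor withdraws the display in 13.4.3.

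**The concern.** The trial is sized for one overall difference of 25 points. Split by a covariate, each interval becomes wide relative to that effect, and whether it crosses zero is then largely chance. If nobody has said how the plot is to be read, a common informal reading is that the diet difference is present where the interval excludes zero and absent where it does not. That can produce an apparent subgroup finding when there is none.

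The question matters in this trial. Protocol section 3.1 hypothesises that patient phenotypes relate to response to each intervention, and the practical interest lies in who can use the less restrictive diet. A false impression that the advantage of 6FED is confined to one sex, or to atopic patients, would be easy to take from such a plot.

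**Working it through.** **Inputs.** From protocol 13.6: remission 45% on 1FED and 70% on 6FED; 60 per group before and 68 per group after the drop-out allowance. From 13.4.1: missing outcomes count as failures, so all 68 per group enter the analysis. From 13.4.3: two-sided 5%, rate differences with 95% CIs. The documents give no subgroup shares, so splits of 50:50, 70:30 and 80:20 are assumptions, with the same rates in both levels and the diets balanced within levels.

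**The plan's own figure.** Section 13.6 states that 60 per group "will provide at least 80% power to detect a difference in rates between groups of 25" percentage points. A normal approximation gives 79.9%, and exact enumeration of the likelihood ratio test gives 80.6%. The figure reproduces.

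**Width of one subgroup interval.** The variance sum is 0.45×0.55 + 0.70×0.30 = 0.4575. With 34 per group in a level, half-width = 1.96 × √(0.4575/34) = 22.7 points.

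**Reading 1: which intervals exclude zero.** Let A and B be the chances that the interval in each level excludes zero. The chance that exactly one does is A(1−B) + B(1−A). Exact Wald intervals, 68 per group:

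| Split | n per group in each level | A | B | Exactly one excludes zero |
|---|---|---|---|---|
| 50:50 | 34 / 34 | 0.604 | 0.604 | 47.8% |
| 70:30 | 48 / 20 | 0.711 | 0.441 | 52.5% |
| 80:20 | 54 / 14 | 0.782 | 0.355 | 58.2% |

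For the even split: 2 × 0.604 × 0.396 = 0.478. Variations at 50:50:
- normal approximation, 68 per group: 49.5%
- Newcombe intervals, 68 per group: 48.8% (and 56.3% at 70:30, 63.1% at 80:20)
- 60 per group, exact Wald: 50.0%
- drop-outs counted as failures, assumed rates 45×60/68 = 39.7% and 70×60/68 = 61.8%: 50.0%

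With three independent even-split factors (68 per group, simulated), at least one looks discordant in about 74% of trials.

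**Other readings of the same plot.** Simulation of 400,000 trials, identical effects, 68 per group:

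| Reading | 50:50 | 80:20 |
|---|---|---|
| The two intervals do not overlap | 0.8% | 1.5% |
| A subgroup interval excludes the overall estimate | 1.2% | 4.6% |
| Point estimates have opposite signs | 2.4% | 6.2% |
| Interaction test, rate difference | 5.7% | 6.6% |
| Interaction test, log odds | 4.6% | 3.9% |

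**Precision of the interaction estimate, 50:50.** SE = √(0.4575/34 + 0.4575/34) = 16.4 points. The 95% CI is ±1.96 × 16.4 = ±32 points, and the difference between subgroup effects detectable with 80% power is 2.80 × 16.4 = 46 points. At 60 per group these become ±34 and 49 points.

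**The case against.** The strongest reply is that the documents do not tell anyone to compare which intervals cross zero. A reader might infer that the planned method itself looks inconsistent about half the time. The documents do not support that: they ask for a visual examination and prescribe no rule. Judged by overlap, the same plot raises a false alarm in about 1% of trials. This reply stands, and the figure of about one half has to be tied to the one reading that produces it. What remains is that the plan leaves the reading open, so the false-alarm rate can be near 1% or near 50%.

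A reader might also extend the argument to the Phase 2 plots in protocol 13.4.4, of which the protocol says "This will provide a visual representation to assess consistency of rates across subgroups". Those plots show remission rates within a single treatment group. Zero is not a reference value there, and the percentages above do not carry over. No point is made about them.

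Two further replies stand in part. The stakes are limited: the plots are supportive, no subgroup claim is planned, and neither the primary test nor the sample size depends on them. And an interaction estimate is weak here, since the detectable difference of 46 points is nearly twice the design effect of 25. Treating a non-significant interaction as proof of consistency would exchange false alarms for false reassurance. That limits how the estimate may be used, but it is no reason to omit it.

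**Conclusion.** The point holds in a limited form. Visual inspection of separate subgroup intervals is the only stated method, no diet-by-subgroup estimate or reading rule accompanies it, and the SAP leaves open whether the display is still planned. Under an identical effect, a reader who goes by zero-crossing would see a discrepancy in about 48-50% of trials for an even split and about 52-58% for 70:30 to 80:20 splits with exact Wald intervals; Newcombe intervals put the uneven splits somewhat higher. Reading by overlap gives about 1%, and a direct interaction test about 4-6% for an even split.

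These figures rest on the planning rates of 45% and 70%, 68 per group (60 changes little), and assumed subgroup shares. The severity is a change to consider: it improves reporting and does not touch the primary conclusion.

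**What to change.** 1. State in the SAP whether the subgroup forest plots of protocol 13.4.3 are kept or dropped.
2. If kept, list the subgroup covariates. For each two-level covariate, print the difference between the subgroup rate differences, which is the plotted scale, with its 95% CI and interaction p-value. For a covariate with more levels, give the contrasts with a named reference level and one overall interaction p-value.
3. Optionally add the diet-by-covariate term from the mixed logistic model, labelled as being on the log-odds scale, because the two scales can disagree.
4. State that differences between subgroups are read from that estimate and not from which intervals cross zero, that it is reported as an estimate, and that a non-significant result is not evidence of consistency.

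The cost is one contrast or model term per covariate and a few sentences, with no new data. The downside is imprecision: about ±32 points for an even split and wider for uneven ones, so the estimate will rarely settle the question.

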13.4.4 Analyses of Secondary and Other Endpoint(s)/Outcome(s)

Following are the secondary objectives of the study:

1. To extend Phase 1 of this study with a prospective non-blinded trial that determines the rate of remission following SGC in the 6FED non-responders and the rate of remission following 6FED in the 1FED non-responders (Phase 2).
2. To evaluate the effect of each therapy on histological remission defined by a variety of changes in eosinophils, including (a) pre- and post-therapy peak eosinophil counts; (b) partial remission (2-14 peak eosinophils/hpf); and (c) complete histological remission (≤ 1 peak eosinophils/hpf).
3. To evaluate the effect of each therapy by utilizing the histology scoring system (HSS) created to express the severity and extent of other abnormalities in the gastrointestinal (GI) tract that often accompany eosinophilic inflammation.
4. To evaluate endoscopic outcomes as assessed by the endoscopy scoring system (EREFS).
5. To determine the impact of each therapeutic intervention on biomarkers using the EoE Diagnostic Panel (EDP).

For secondary objective 1, the remission rate for non-responders who proceed to Phase 2 will be summarized separately depending on the treatment patients received during Phase 1. The 95% two-sided confidence interval for the rate will be provided. In addition, forest plots that display the estimated remission rate along with two-sided 95% confidence interval will be presented for the subgroups as defined for the primary endpoint. This will provide a visual representation to assess consistency of rates across subgroups. If the remission rate is missing for patients in Phase 2, it will be imputed as a treatment failure.

The formal statistical hypothesis for each of the key secondary endpoint is:

$$H_0: \theta_{1FED} = \theta_{6FED}$$

$$H_1: \theta_{1FED} \neq \theta_{6FED}$$

where

θ_{1FED} =population parameter (e.g. mean, proportion) for patients in histologic remission (<15 eosinophils/hpf) on the 1FED diet at end of Phase 1

θ_{6FED} =population parameter (e.g. mean, proportion) for patients in histologic remission (<15 eosinophils/hpf) on the 6FED diet at end of Phase 1.

To test these hypotheses for each of the secondary objectives 2-5, treatment group comparisons at the end of Phase 1 will be performed using the generalized linear mixed effects model using the link that is appropriate for the endpoint (i.e. logit for binary, cumulative logit for ordered multinomial categories, identity for continuous). These models will account for the clustering within sites and will include gender, presence of atopy and duration of disease as covariates. For continuous data, appropriate transformations will be considered (e.g. log, square root,

rank) to satisfy the assumptions of the analyses. If the remission status for the categorical outcomes is missing, it will be imputed as a treatment failure. Missing data for continuous outcomes will be imputed using multiple imputation techniques. Covariates for imputation will include investigative site, gender, presence of atopy and duration of disease. Each of the secondary outcomes 2-5 will be tested at the two-sided $\alpha=0.01$ to account for multiple testing.

13.4.5 Analyses of Exploratory Endpoint(s)/Outcome(s)

Exploratory objectives are detailed below:

1. To evaluate the clinical and psychosocial effect of each therapy utilizing surveys to assess EoE symptoms and problems/feelings related to eating.
2. To determine if any clinical parameters predict response to therapeutic intervention.
3. To determine if any biomarkers including serum food specific IgE, CRD, and IgG4 predict response to therapeutic intervention.
4. To determine if skin testing, in the form of prick and patch testing, predicts response to therapeutic intervention.
5. To determine if milk-driven T cells in the blood positively correlate with milk atopy patch test results and effectiveness of dietary therapies.

At the start of the trial intake of the allergens will be determined and descriptive statistics will be used to describe how often/how much of the allergens were consumed as part of the usual diet. During the trial any accidental exposure will be documented and we can use descriptive statistics to describe how often/how much of the allergens were consumed accidentally.

To compare treatment groups at the end of Phase 1 for EoE symptoms and problems/ feelings related to eating, the generalized linear mixed effects model described for the secondary endpoints will be used with the link function appropriate for the endpoint. Imputation for missing data will follow that described for the secondary endpoints.

To evaluate the ability of biomarkers to predict response to therapeutic intervention, multivariable logistic regression analysis will be conducted with remission/no remission as the dependent variable and biomarker levels as the independent variables. Multi-collinearity of the independent variables will be assessed. The area under the receiver operating characteristic curve (AUROC) will be estimated along with 95% confidence interval. This analysis will be conducted based on the remission status at the end of Phase 1. This analytic approach will be used to determine if skin testing predicts response to therapeutic intervention and to determine if milk-driven T cells predict response to intervention and to determine if T cells correlate with milk atopy patch test results. All exploratory analyses will be conducted at the nominal two-sided $\alpha=0.05$.

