debate about its practice in managing EoE. As such, in this sub-aim, we will take several different approaches compared with prior work. In particular, we will be conducting a multi-site trial and have the advantage that we can standardize the skin testing procedure, by using agreed upon techniques, including food extracts, skin test reagents, and measurement parameters. We will thus be in a good position to dissect discrepant results between centers. Furthermore, our trial is unique in that half of the patients will undergo a milk elimination diet as part of the first phase. Thus, we will be in a position to focus on the value of skin testing for milk, which is particularly attractive as milk is the number one food trigger of EoE¹⁹. It is important to point out that although skin testing (including patch testing) is now readily performed in EoE, there have been no studies that have assessed the local response. For example, it has not yet even been determined if positive responses involve immunological reactions, so basic cytokine and histological analyses are likely to be fundamentally informative.

- 2c. Serum food specific IgE, CRD, and IgG4.** The level of food specific IgE, CRD, and IgG4 will be determined by a solid phase immunoabsorbent assay (ELISA) focusing on the 6FED foods. Serum will be banked and processed in batches. Component testing for at least each of the 6 foods will be performed as feasible. The Investigators reserve the right to perform these analyses using commercially available platforms including UniCAP and the Immuno Solid-phase Allergen Chip (ISAC, Thermo Scientific).

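### The protocol's exploratory marker AUROC has no internal validation and is biased upward by an amount that depends on an unstated number of markers; the SAP omits it without withdrawing it

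*Protocol*

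**What the plan says.** Protocol 13.4.5 sets out the prediction analysis: "multivariable logistic regression analysis will be conducted with remission/no remission as the dependent variable and biomarker levels as the independent variables". Collinearity among the markers is to be assessed. Performance is then summarised: "The area under the receiver operating characteristic curve (AUROC) will be estimated along with 95% confidence interval". The outcome is fixed: "This analysis will be conducted based on the remission status at the end of Phase 1". The method is carried over to other marker families, first to skin tests ("This analytic approach will be used to determine if skin testing predicts response to therapeutic intervention") and then to milk-driven T cells. On error control the section says "All exploratory analyses will be conducted at the nominal two-sided" 0.05 level.

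The candidate markers are described elsewhere:

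- Protocol 4.4, sub-aim 2c, covers food-specific IgE, IgG4 and component tests for the six-food diet, and adds: "Component testing for at least each of the 6 foods will be performed as feasible".
- The SAP's list of exploratory variables names skin prick tests to seven foods and five tree nuts.
- Protocol 4.4, sub-aim 2d, limits the T-cell work to a pilot in 1FED patients.

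The SAP of 10/14/2019 covers the same objective by comparing responders with non-responders in generalized linear mixed models. It mentions neither an AUROC nor any validation step, and it does not say that the protocol's AUROC is dropped.

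**The concern.** A logistic model chooses its coefficients to separate the remitters from the non-remitters it is given. An AUROC computed on those same patients gives the model credit for fitting chance differences. An ordinary confidence interval does not correct this, because it treats the fitted score as if it had been fixed beforehand. The more markers there are per patient, the larger the excess.

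At stake is the reading of the exploratory results. Protocol 3.1 hypothesises that skin tests will predict the outcome of the diet phases. An AUROC near 0.7 with an interval clear of 0.5 would be taken as support for that kind of claim, and uninformative markers could produce it.

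**Working it through.** **Inputs from the documents** (Protocol 13.6 unless noted)

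- Planned remission: 45% on 1FED and 70% on 6FED. With 1:1 allocation the pooled rate is (45 + 70)/2 = 57.5%.
- Sample size: 60 per group for 80% power, raised to 68 per group, 136 in total.
- Prick tests (SAP): 7 foods + 5 tree nuts = 12.
- Serum markers (Protocol 4.4, 2c): IgE, IgG4 and at least one component for each of six foods = 3 × 6 = 18, if every food enters separately.

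**Input not in the documents.** The number of markers k entering each model is an assumption, so the range 1 to 18 is shown.

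**The plan's own figure.** The plan states no AUROC, predictor count or precision target. The figure that bears on this point is the sample size. Exact enumeration of the likelihood ratio test at 60 per group, 45% against 70%, gives power 0.806, and the normal approximation gives 0.799. The stated 60 per group reproduces.

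**Information per marker.** Expected non-remissions at N = 136 are 136 × (1 − 0.575) = 57.8. That is 57.8/12 = 4.8 per marker at k = 12 and 57.8/18 = 3.2 at k = 18.

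**Simulation.** There were 1,000 trials per setting. Each had k independent standard normal markers, with remission drawn at the planned rate regardless of the markers. The model was logit P(remission) = b0 + b1x1 + … + bkxk, fitted by maximum likelihood. The apparent AUROC is the share of remitter/non-remitter pairs in which the remitter has the higher fitted score. The interval is AUROC ± 1.96 × DeLong standard error.

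| k | Apparent AUROC, N = 136 | Intervals wholly above 0.5 | Apparent AUROC, 1FED arm, N = 68 | Intervals wholly above 0.5 |
|---|---|---|---|---|
| 1 | 0.540 | 5% | 0.553 | 5% |
| 3 | 0.580 | 29% | 0.608 | 27% |
| 6 | 0.617 | 68% | 0.668 | 74% |
| 12 | 0.669 | 98% | 0.743 | 98% |
| 18 | 0.709 | 100% | 0.805 | 100% |

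Scored on 2,000 new patients, the same fitted models gave an AUROC of 0.50 in every setting.

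**Hand check.** For noise markers the squared standardised separation of the fitted score is roughly D² = k(1/n1 + 1/n0), and AUROC ≈ Φ(√(D²/2)). With n1 = 136 × 0.575 = 78.2 and n0 = 57.8, 1/n1 + 1/n0 = 0.0301.

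- k = 6: Φ(√(0.181/2)) = Φ(0.300) = 0.618
- k = 12: Φ(√(0.361/2)) = Φ(0.425) = 0.665
- k = 18: Φ(√(0.542/2)) = Φ(0.520) = 0.699

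These agree closely with the simulation.

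**Sensitivity.**

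- Hanley-McNeil intervals lay above 0.5 in 71%, 99% and 100% of trials for 6, 12 and 18 markers at N = 136.
- A repeat run gave 34% at 3 markers and 96% at 12, hence the rounded figures of about 30% and 97%.
- With markers correlated at 0.6, including skewed and 20%-positive binary versions, N = 136 and k = 12 gave 0.65 to 0.67, with 94% to 98% of intervals above 0.5. With k = 6 it gave 0.60 to 0.62 and 52% to 70%.
- With 120 evaluable patients, k = 12 gave 0.682 (98%) and k = 18 gave 0.726 (100%).

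**What removes the bias** (noise markers, true value 0.50, N = 136)

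| k | Apparent | Bootstrap optimism-corrected | 10-fold cross-validated |
|---|---|---|---|
| 6 | 0.617 | 0.537 | 0.476 |
| 12 | 0.669 | 0.558 | 0.488 |
| 18 | 0.709 | 0.568 | 0.490 |

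Repeated 10-fold cross-validation gave 0.47 to 0.49, with 3% to 8% of intervals above 0.5. Bootstrap intervals that refit the model did not work. With 6 noise markers the percentile interval excluded 0.5 in 100% of trials. Shifted by the estimated optimism, it still did so in 48% (6 markers) and 89% (12 markers).

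**The case against.** The strongest reply is that the later SAP handles this objective differently. It lists identity and cumulative logit links for comparing responders with non-responders. Since response is binary, those links fit best if each marker in turn is the dependent variable. That is a marker-by-marker comparison, with no combined score and no AUROC to be optimistic. This stands as far as it goes. But the SAP does not withdraw the protocol's AUROC, so a reader cannot tell whether it will be reported.

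The second reply is that the number of markers is unknown. This also stands. With one marker the optimism is small and the interval errs about 5% of the time. The collinearity check might shorten the list, and parts of the plan are milk-only. A reader might infer that the plan is bound to make noise look predictive, or that one model will hold serum markers, skin tests and T cells together. The documents support neither. No marker count is given, and 13.4.5 reads most naturally as a separate analysis for each marker family.

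Third, in-sample estimation is inferred from silence, and no interval method is named. That is true, but no other data or resampling is offered for this model.

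Fourth, a reader might tie the problem to the aim of triaging patients between therapies. That language belongs to sub-aim 2e, the transcript analysis, which has its own text on replication and multiple-testing correction. It should not be used to raise the stakes here. Equally, that text does not answer this point: it concerns the fluticasone gene screen, and corrections for multiple p-values do not remove AUROC optimism.

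**Conclusion.** The concern holds for Protocol 13.4.5 on its natural reading. An AUROC and interval taken from the fitting data would be too high. At N = 136 the excess over a true 0.50 runs from 0.04 with one marker to about 0.21 with 18. Intervals that wrongly exclude 0.5 run from about 5% to 100%. The 12 prick tests, or IgE, IgG4 and components for six foods, would reach the upper part of that range if entered in full.

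The figures assume pure-noise markers, the planned remission rates, a maximum-likelihood fit without pre-selection, and a marker count that the documents do not give. They describe the null case only and do not show how far a real signal would be overstated.

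The consequence is limited. The analysis is labelled exploratory, and the primary and secondary conclusions do not depend on it.

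**What to change.** Reconcile Protocol 13.4.5 with the SAP's section on exploratory endpoints. Either state in the SAP that the AUROC is dropped, or keep it and add:

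- the predictor list for each marker family, fixed before the outcome data are examined;
- a repeated 10-fold cross-validated AUROC as the reported figure, in place of the apparent one;
- an interval based on the cross-validated predictions, not a bootstrap interval;
- any marker selection or penalisation repeated inside each fold.

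The cost is a little more code and no new data. Reported AUROCs will be lower and slightly conservative: with noise markers, single-run 10-fold cross-validation gave 0.476 to 0.490 at N = 136, and 0.454 (6 markers) and 0.474 (12 markers) in the 1FED arm at N = 68.
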